**Table 5 Normal ABPM ranges**

Parameter	ABPM normal reference ranges
Day/Night/24-hours SBP	70 - 240 mmHg
Day/Night/24-hours DBP	40 - 150 mmHg
Pulse Pressure (PP)	20 - 150 mmHg
Mean Arterial Pressure (MAP)	40 - 200 mmHg
Day/Night/24-hours HR	20 - 200 bpm

### 3.6 Safety variables

Safety and tolerability of MEDI7352 will be evaluated based on the AEs, physical and neurological examination, total neuropathy scores, vital signs, survey of autonomic symptoms, electrocardiograms, injection site reactions, radiographic and magnetic resonance imaging assessment and clinical laboratory assessment.

#### 3.6.1 Adverse events

AEs and serious AEs (SAEs) as defined in the protocol appendix C will be collected from the screening, throughout the study, and including the follow-up period. The Medical Dictionary for Regulatory Activities (MedDRA) will be used to code the AEs, using the latest version. AEs will be graded according to the Common Terminology Criteria for AEs (CTCAE version 5).

A treatment emergent adverse event (TEAE) is defined as:

- any AE with an onset at the time of or following the start of study treatment through the end of study participation as per DS page in eCRF;

- any AE starting prior to the start of study treatment administration but increasing in severity at the time of, or following, the start of study treatment through end of study participation as per DS page in eCRF.

Any AE occurring before the first dose of study treatment and without worsening after the first dose will be included in the data listings but will not be included in the AE summary tables.

The causal relationship between IP and each AE will be recorded. For SAEs, causal relationship will be assessed for other medication and study procedures.

### **3.6.1.1 Adverse events of special interest**

An AE of special interest (AESI) is one of scientific and medical interest specific to understanding of the IP and may require close monitoring and collecting additional information by the investigator. An AESI may be serious or nonserious. The rapid reporting of AESIs allows ongoing surveillance of these events to characterise and understand them in association with the use of MEDI7352.

AESIs for MEDI7352 include, but are not limited to:

- Positively-adjudicated possible or probable Rapidly Progressive Osteoarthritis (RPOA), Subchondral Insufficiency Fracture (SIF), primary osteonecrosis, or pathological fracture
- Infections that meet SAE or severe AE criteria (see CSP Appendix C 2)
- Anaphylactic reactions; serious or severe hypersensitivity reactions; or injection site reactions that lead to permanent discontinuation of administration of IP
- Other – includes AESIs that do not meet any of the above criteria, but are deemed of interest by the study team

AESIs irrespective of their severity and seriousness should be reported immediately using the same procedure as for SAE reporting (See CSP section 8.3.9).

### **3.6.1.2 Adverse events based on signs and symptoms**

All AEs spontaneously reported by the participant or care provider or reported in response to the open question from the study site staff: 'Have you had any health problems since the previous visit/since you were last asked?' or revealed by observation will be collected and recorded in the eCRF.

### **3.6.1.3 Adverse events based on examinations and tests**

Deterioration as compared to baseline in protocol-mandated laboratory values and vital signs will only be reported as AEs if they fulfil any of the SAE criteria, are the reason for discontinuation of treatment with the IP or are considered to be clinically relevant as judged by the investigator (see CSP section 8.3.7).

In addition, occurrences in liver biochemistry of AST or ALT  $\geq 3 \times$  ULN together with total bilirubin  $\geq 2 \times$  ULN will be reported as SAEs as per Hy's Law (see CSP Appendix F).

### **3.6.1.4 Pregnancy**

Abnormal pregnancy outcomes (e.g., spontaneous abortion, foetal death, stillbirth, congenital anomalies, and ectopic pregnancy) are considered SAEs. A woman who becomes pregnant during IP treatment or within 30 days of discontinuing the IP will be immediately withdrawn from study participation. Every pregnancy will be documented in EDC using the pregnancy report (PREGREP) page in eCRF.

## **3.6.2 Physical examination**

The following assessments will be performed as part of the physical examination:

General appearance, skin, head and neck, examination of the oral cavity for any lesions, lymph nodes, thyroid, abdomen (bowel sounds, liver, and spleen palpation), back (including costovertebral angle tenderness), musculoskeletal/extremities, cardiovascular, and respiratory systems.

The physical examination will be performed during screening, treatment period and follow-up period, as indicated in CSP (Table 1).

### **3.6.2.1 Weight**

Weight will be measured at screening and at Week 12 as well as when change is suspected, or fluid retention occurs.

## **3.6.3 Neurological examination**

The neurological examination performed ideally by a neurologist include:

Assessment of mental status, cranial nerves, motor examination (muscle strength and tone), upper and lower extremity deep tendon reflexes, plantar responses, sensory system examination, coordination, and gait.

The neurological examination will be performed during screening, treatment period and follow-up period, as indicated in CSP (Table 1).

For participants with clinical manifestations consistent with worsening of pre-existing neuropathy, follow-up nerve conduction studies should be performed and documented at the time points deemed appropriate by the neurologist, but at least once during participation in the study.

### **3.6.4 Total neuropathy score- nurse (TNSn) variables**

The total neuropathy score – nurse (TNSn) assessment is collected as scores as follows:

- Sensory symptom score
  - Sensory symptoms consist of six questions, each rated from 0 to 4.
  - Sensory symptom score is determined as the maximum of the six scores.
- Motor symptom score
  - Motor symptoms consist of four questions, each rated from 0 to 4.
  - Motor symptom score is determined as the maximum of the four scores.
- Autonomic symptom score
  - Autonomic symptoms consist of six symptoms rated as present or not (yes/no)
  - Autonomic symptom score is determined as the number of symptoms present, with a maximum score of 4 assigned for four or more symptoms present.
- Pin sensibility score
  - Pin sensibility is scored as 0 to 4 in upper and lower limbs both left and right, therefore four areas in total.
  - Pin sensibility score is determined as the maximum of the four scores.
- Vibration sensibility score
  - Vibration sensibility is scored as 0 to 4 in upper and lower limbs both left and right, therefore four areas in total.
  - Vibration sensibility score is determined as the maximum of the four scores.
- TNSn total
  - The total score is determined as the sum of the five aforementioned scores.

The TNSn assessment will be performed during screening, treatment period and follow-up period, as indicated in CSP (Table 1).

The ET assessments will be handled in the same manner as for primary endpoint that is will be reassigned based on the study day.

### 3.6.5 Vital Signs

Blood pressure (BP) and pulse rate will be measured at each clinic visit with details about the method, time and frequency described in CSP section 8.2.3.1. Body temperature and respiratory rates will be measured at different time points as indicated in CSP (Table 1).

Absolute values will be compared to the reference ranges in [Table 6](#) and classified as low (below range), normal (within range or on limits) or high (above range). All values (absolute) falling outside the reference ranges will be flagged.

**Table 6 Vital signs reference ranges**

Parameter	Standard Unit	Lower Limit	Upper Limit
Diastolic Blood Pressure	mmHg	60	120
Systolic Blood Pressure	mmHg	100	160
Pulse Rate	Beats/min	40	120
Respiratory Rate	Breaths/Min	8	28
Body Temperature	Celsius	36.5	38

#### 3.6.5.1 Orthostatic blood pressure

Orthostatic (BP) measurements will be obtained at all clinic visits and taken after scheduled supine measurements (1 and 3 minutes after the participant stands) and prior to any required blood draw or study treatment administration (and prior to randomisation on Day 1).

After stable BP is achieved in supine position (see CSP section 8.2.3.2), the participant will stand, and a BP measurement will be taken at 1 and 3 minutes after the participant stands. If the BP measurements also referred to as postural changes do not meet the criteria for orthostatic hypotension, no additional measurement is needed. If the BP measurement meets any of the criteria shown in CSP Table 6, investigators will repeat the supine and standing measurements up to 2 additional times. Blood pressure changes meeting the pre-specified criteria and confirmed will be designated as a confirmed orthostatic hypotension episode.

### 3.6.6 Survey of Autonomic Symptoms (SAS)

The SAS is an instrument that measures autonomic symptoms used for assessing autonomic neuropathies in clinical trials.

The SAS evaluates the presence of a symptom and the degree of its severity. It consists of 11 questions in women and 12 in men.

Each question has a “Yes” or “No” answer to symptoms occurring 6 months prior to IP administration. Questions answered with “Yes” are further rated from 1 to 5 by asking the

participant how much each symptom is bothering him or her. Each answer is scored on a scale from 1 to 5 where 1 = “not at all” and 5 = “a lot”, and a total symptom impact score is determined as the sum of the ratings provided for all reported symptoms, that is questions answered with ‘Yes’.

The following domains are assessed:

Orthostatic, sudomotor symptoms, vasomotor, gastrointestinal, urinary, and sexual dysfunction.

The assessment is done at Day 1 and Week 36 only.

### **3.6.7 Electrocardiograms**

Electrocardiograms (ECGs) will be obtained during screening, during treatment period and follow-up period as indicated in CSP (Table 1).

The investigator will judge the overall interpretation as normal or abnormal clinically non-significant or abnormal clinically significant, and this evaluation will be reported in the eCRF.

### **3.6.8 Laboratory data**

Blood and urine samples for determination of clinical chemistry, haematology, coagulation, serology, drug screening, pregnancy tests, and urinalysis will be taken at the visits indicated in CSP Table 1.

Blood and urine samples for haematology, serum chemistry, coagulation, urinalysis, and serology will be sent to a central laboratory for analysis. Urine drug screens will be conducted at the study sites. Serum pregnancy test will be conducted at the central laboratory; urine pregnancy test will be conducted at study sites.

Samples for laboratory tests will include the following:

- Haematology: haemoglobin, haematocrit, red blood cell (RBC) count, RBC indices, mean corpuscular haemoglobin, mean corpuscular haemoglobin concentration, platelet count (or estimate), white blood cell count, and white blood cell differential
- Serum chemistry: albumin, total and direct bilirubin, total protein, calcium, alkaline phosphatase (ALP), alanine aminotransferase (ALT), aspartate aminotransferase (AST), gamma glutamyl transferase (GGT), blood urea nitrogen (BUN), creatinine\*, glucose, sodium, potassium, chloride, bicarbonate, calcium, phosphorus, lactate dehydrogenase (LDH), uric acid, C-reactive protein (CRP), cholesterol, triglycerides, creatine phosphokinase.
- Coagulation panel: prothrombin time, activated partial thromboplastin time, fibrinogen
- Urinalysis: pH, specific gravity, blood, leukocytes, glucose, protein, ketones, bilirubin

- Urine drug screen: including but not limited to amphetamine, barbiturate, cannabinoids, cocaine, methadone, methaqualone, opiate, phencyclidine, and propoxyphene.
- Urine pregnancy test (only in female participants not surgically sterile)
- Serology: human immunodeficiency virus (HIV), hepatitis B, and hepatitis C screen, tuberculosis (TB) (QuantiFERON), and anti-citrullinated protein antibodies (ACPA) (screening only)
- Endocrinology: follicle-stimulating hormone (FSH) (Female < 50 years of age only and at screening only, to confirm menopausal state),  $\beta$ -HCG beta human chorionic gonadotropin (female participants, not surgically sterile only, at screening only).
- Other: haemoglobin A1c

\*Note: Serum chemistry reports should include calculation of creatinine clearance using the Cockcroft-Gault equation.

HIV, hepatitis B and C and TB QuantiFERON data is considered sensitive and as such, the data will remain at the sites and will not be transferred further hence will not be part of the analysis.

Change from baseline in hematology, chemistry, coagulation, urinalysis, and haemoglobin A1c variables will be calculated for each post-dose visit as per the protocol defined schedule.

### **3.6.9 Injection site reactions**

Injection site reactions occurring during or immediately following study treatment administration will be evaluated. Local reaction to injectable product will be evaluated for pain, tenderness, erythema/redness, and induration/swelling, and classified as mild, moderate or severe as per CSP (Table 7).

In addition,

- For erythema/redness, the measurement associated to the local reaction at the greatest single diameter should be recorded as a continuous variable.
- Induration/swelling should be evaluated as the actual measurement.

### **3.6.10 Radiographic (X-ray) and magnetic resonance imaging (MRI) assessments**

#### **3.6.10.1 X-ray assessments**

All participants should undergo diagnostic x-ray on the shoulder, knee, and hip joints during screening period while at Week 32 visit, x-ray imaging is performed on the knee and hip joints. Any potentially clinically significant findings detected on X-ray performed at week 32 will be further assessed and sent for adjudication. In addition, unscheduled X-ray should be performed “for cause” to follow up on any worsening symptoms. These assessments will aid

identification of joint safety events such as RPOA, SIF, primary osteonecrosis, or pathological fractures.

**3.6.10.2 MRI assessments**

MRI of the bilateral knee joints must be done during screening period unless participant undergone a total joint replacement and has an artificial nontarget joint or when a knee joint is no longer present due to leg amputation. In addition, unscheduled MRIs should be done “for cause” in the knee joints or the joints with a KL grade at baseline of  $\geq 3$ .

**3.6.11 Study treatments**

Study treatment in this study refers to MEDI7352, and placebo. See [Table 7](#) for further details.

**Table 7 Study treatments**

	Study treatment name	Route of administration	Dosing instructions
Active	MEDI7352	CCI	CCI
Placebo	Saline solution		0.9% (w/v) saline q2w.

CCI ; q2w Every 2 weeks; CCI

**3.6.11.1 Exposure of study treatment**

Exposure (i.e. duration of treatment) will be defined as follows:

*Total (or intended) exposure of study treatment in days*

- Total (or intended) exposure = min (last dose date + 13 days or date of death) – (first dose date) +1

The total participant years of exposure is the sum of duration of exposure (days) of all participants in the respective treatment group divided by 365.25 (years).

**3.6.11.2 Compliance**

Study treatment compliance with IP administration is calculated as:

$$(\text{Total doses administered} / \text{total doses expected}) \times 100.$$

The total number of doses expected includes all visits with protocol scheduled IP administration before a participant's Week 12 (EOT/ET) visit.

## 4 ANALYSIS METHODS

Formal statistical testing of the primary and key secondary efficacy endpoints with maintaining overall family-wise type-I error at 1-sided 2.5% level will be performed as follows:

### Multiple comparison procedure-modelling (MCP-Mod) statistical tests

The main hypothesis tested:

- $H_0$ : No dose-response effect, i.e., the linear contrasts of group means corresponding to each of the 6 pre-specified candidate dose-response models are all identically zero.
- $H_1$ : Dose-response effect, i.e., at least one of the linear contrasts of group means corresponding to each of the 6 pre-specified candidate dose-response models differs to zero.

The individual test statistic and corresponding p-value for each candidate model are calculated by following steps 1-3 in section 4.2.1.2.1.1.

The minimum of the multiplicity adjusted p-value corresponding to each candidate model will be used as the basis for concluding statistical significance.

### Pairwise statistical tests

There will be 4 treatment comparisons:

- MEDI7352 CCI vs placebo
- MEDI7352 CCI vs placebo
- MEDI7352 CCI vs placebo
- MEDI7352 CCI vs placebo

For each pairwise comparison, the following hypothesis will be tested:

- $H_0$ : No difference between MEDI7352 and placebo
- $H_1$ : Difference between MEDI7352 and placebo

However, pairwise testing of only two highest doses (MEDI7352 CCI and MEDI7352 CCI) versus placebo of the primary and key secondary endpoints will undergo formal statistical testing.

The testing process will commence with the primary endpoint followed by key secondary endpoints using a sequentially rejective multiple comparison approach detailed in section 4.2.1.1.

## 4.1 General principles

Efficacy outputs will be presented by cohorts also referred to as the treatment arms, while safety outputs will also include ‘MEDI7352 Total’ defined as the sum of all MEDI7352 cohorts. Study population outputs will be presented by cohorts, MEDI7352 Total and Total (defined as all MEDI7352 cohorts + placebo), except otherwise specified.

The below mentioned general principles will be followed throughout the study:

- Descriptive statistics will be used for all variables, as appropriate, and will be presented by cohort. Continuous variables will be summarised by the number of observations, mean, standard deviation (SD), median, minimum, and maximum. Categorical variables will be summarised by frequency counts and percentages for each category.
- Unless otherwise stated, percentages will be calculated out of the analysis set total for the corresponding cohort.
- For continuous data, the mean and median will be rounded to 1 additional decimal place compared to the original data. The SD will be rounded to 2 additional decimal places compared to the original data. Minimum and maximum will be displayed with the same accuracy as the original data unless otherwise stated.
- For categorical data, percentages will be rounded to 1 decimal place.
- Results of all statistical analysis will be presented using a 95% confidence interval (CI) and 1-sided p-value, unless otherwise stated.
- P-values will be rounded to 3 decimal places, except p-values less than 0.0005 (e.g. 0.0002) will be displayed as <0.001. P-values outputted as <0.0001 by statistical software will not be modified, hence displayed as ‘<0.0001’.
- SAS® version 9.4 or higher will be used for all analyses.

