### **3.1.4 Early termination visit**

Assessments associated with an early termination of IP are the same as those for EOT (Week 12) visit. Consequently, summaries presented by visit will not differentiate whether the Week 12 assessments correspond to the EOT or the ET visit. The exceptions are the primary endpoint, secondary endpoints, **CCI**, TNSn and DSIS for which the handling of the data associated with ET visit can be found in sections 3.2, 3.3, 3.6.4 and 3.5.1.1 respectively.

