#### **4.2.6 Safety analysis**

Safety summaries will be descriptive only. No formal statistical analyses are planned for safety data. All data will be reported using the safety population unless specified otherwise.

The following sections describe the planned safety summaries for safety variables as defined in section 3.6. However, additional safety summaries (not specified in this SAP) may need to be produced to aid interpretation of the safety data.

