#### 4.2.6.4.1 Liver enzyme elevations and Hy's law

Liver function laboratory tests assessments (scheduled and unscheduled) up to 30 days after the last dose of study treatment will be considered.

The following summaries will include the number (%) of participants with at least one post-baseline liver function assessment who have:

- Elevated ALT, AST and total bilirubin as
  - ALT  $\geq 3\times$  to  $<5\times$ ,  $\geq 5\times$  to  $<10\times$ ,  $\geq 10\times$  to  $<20\times$ ,  $\geq 20\times$  upper limit of normal (ULN)
  - AST  $\geq 3\times$  to  $<5\times$ ,  $\geq 5\times$  to  $<10\times$ ,  $\geq 10\times$  to  $<20\times$ ,  $\geq 20\times$  ULN
  - Total bilirubin  $\geq 2\times$  ULN
  - ALT or AST  $\geq 3\times$  to  $<5\times$ ,  $\geq 5\times$  to  $<10\times$ ,  $\geq 10\times$  to  $<20\times$ ,  $\geq 20\times$  ULN
  - ALT or AST  $\geq 3\times$  ULN and total bilirubin  $\geq 2\times$  ULN (Potential Hy's law): The onset date of ALT or AST elevation should be prior to or on the date of total bilirubin elevation.

Percentages will be based on the number of participants who have at least one measurement available.

To identify potential Hy's Law cases, a listing of participants who have ALT or AST  $\geq 3\times$  ULN and total bilirubin  $\geq 2\times$  ULN (not necessarily at the same time) following first dose of study treatment will be provided.

A shift table will also present maximum ALT and AST observed values by maximum total bilirubin observed value, expressed as multiples of ULN. Categories will be included for:

- ALT  $<3$ ,  $\geq 3\times$  to  $<5\times$ ,  $\geq 5\times$  to  $<10\times$ ,  $\geq 10\times$  to  $<20\times$ ,  $\geq 20\times$  ULN
- AST  $<3\times$ ,  $\geq 3\times$  to  $<5\times$ ,  $\geq 5\times$  to  $<10\times$ ,  $\geq 10\times$  to  $<20\times$ ,  $\geq 20\times$  ULN
- Total bilirubin  $<2\times$ ,  $\geq 2\times$  ULN

Key participant information table of participants with potential Hy's law will be produced.

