#### 4.2.6.5 Vital signs results

Table with descriptive summaries (n, mean, SD, median, minimum, maximum, Q1 and Q3) of observed values and changes from baseline values for each treatment group at each protocol scheduled time point will be produced for the following vital signs tests:

- Systolic BP
- Diastolic BP
- Pulse rate
- Respiratory rate
- Temperature

In addition, shift table from baseline to minimum/maximum value during treatment will be produced for all above mentioned parameters. The reference ranges provided in section 3.6.5 will be used to determine whether the minimum/maximum value during treatment is within the normal range or not.

A by-visit incidence summary of orthostatic hypotension will be prepared for the following result categories:

- Criteria met
- Confirmed
- Symptomatic

A table presenting the changes in postural BP at each timepoint/ visit will be produced. Consequently, the supine readings from VS (for non-dosing visits) and VS1 (for dosing visits) eCRF forms as well as postural readings from VS2 eCRF form will be summarised descriptively by cohorts at each visit and all available timepoints as per all three eCRF forms. In addition, a listing of confirmed and symptomatic orthostatic hypotension cases will be prepared. The listing will include all participants with at least one assessment indicated as a confirmed or symptomatic case of orthostatic hypotension. All available results will be presented in order to see the change over time.

Vital signs data for participants/parameter with at least one abnormal result for the below mentioned parameters will be listed:

- Systolic BP (Including assessments from VS2 page in the eCRF)
- Diastolic BP (Including assessments from VS2 page in the eCRF)
- Pulse rate
- Respiratory rate
- Temperature

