#### **4.2.6.6 ECG results**

Overall evaluation of electrocardiogram (ECG) will be summarised at each timepoint/visit reporting the number (%) of participants presenting a normal, abnormal not clinically significant or abnormal clinically significant evaluation.

In addition, a listing of abnormal ECG results will be prepared. The listing will include all participants with at least one abnormal value reported. All available results will be presented in order to see the change over time.

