#### **4.2.6.10 Injection site reaction**

An incidence summary by severity (mild, moderate, severe) or presence (yes, no) and visit/timepoint will be prepared for the following injection site reactions:

- Pain (mild, moderate, severe)

- Tenderness (mild, moderate, severe)
- Erythema/redness (mild, moderate, severe)
- Induration/swelling (mild, moderate, severe)
- Necrosis (mild, moderate, severe)
- Ulceration (yes, no)

In addition, the quantitative result for erythema/redness and induration/swelling measurements (cm) will be summarised descriptively by visit/timepoint.

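### By-visit categorical safety percentages use the whole analysis set as denominator, so they mix the event rate with visit attendance

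*SAP*

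**What the plan says.** SAP section 4.1 gives one default for all percentages: "Unless otherwise stated, percentages will be calculated out of the analysis set total for the corresponding cohort". Section 4.2.6 fixes the set for safety outputs: "All data will be reported using the safety population unless specified otherwise".

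Three categorical safety displays are then specified by visit with no denominator of their own:

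- Section 4.2.6.5: "A by-visit incidence summary of orthostatic hypotension will be prepared for the following result categories". The categories are criteria met, confirmed and symptomatic.
- Section 4.2.6.6: "Overall evaluation of electrocardiogram (ECG) will be summarised at each timepoint/visit reporting the number (%) of participants presenting a normal, abnormal not clinically significant", followed by a clinically significant category.
- Section 4.2.6.10: "An incidence summary by severity (mild, moderate, severe) or presence (yes, no) and visit/timepoint will be prepared for the following injection site reactions".

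Section 4.2.6.8 adds a by-visit summary of the neurological assessments. It does not mention percentages, but any shown would fall under the same default.

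Other sections do depart from the default. For liver tests, section 4.2.6.4.1 says: "Percentages will be based on the number of participants who have at least one measurement available". Laboratory shift tables (4.2.6.4) require both baseline and post-baseline data. The ADA category table (4.2.5) uses ADA-evaluable participants. None of these is a visit-level rule for the tables above.

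On attendance, section 1.2 sends participants who permanently stop treatment to an early-termination (ET) visit with the Week 12 assessments, and then into follow-up. Section 3.1.4 says that "summaries presented by visit will not differentiate whether the Week 12 assessments correspond to the EOT or the ET visit", with listed exceptions that include TNSn but not vital signs. Section 3.1.8 applies no visit windowing by default.

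**The concern.** A participant who stops treatment early misses the remaining treatment visits but stays in the safety-set denominator. With the same risk at every visit, the displayed percentage therefore falls as participants leave. It then rises at Week 12, where ET assessments made at various earlier times are counted. A reader of the table could take this pattern for a time course of the drug effect.

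Orthostatic hypotension is the most exposed display. Section 3.6.5.1 has it measured at all clinic visits, and its three categories are all positive, so no row shows how many participants were not examined. If the arms lose participants at different rates, the comparison between arms at a visit is distorted as well.

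**Working it through.** The SAP states no figure on this point, so there is nothing to reproduce. The check is denominator arithmetic.

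**Inputs from the SAP (sections 1.2 and 1.3)**

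- About 350 randomised 1:1:1:1:1, so 350 / 5 = 70 per arm.
- Recruitment stops at information equivalent to 255 completers, or at about 350 randomised, whichever is sooner. 255 / 350 = 72.9%, so 27.1% is used below as an illustrative drop-out level.

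**Assumptions (not in the SAP)**

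- A constant rate p = 5% among those assessed.
- Drop-out D accrues linearly over 12 weeks. D = 27.1%, with 10% and 40% as a range.
- A share a of those who stop attend the ET visit, with a from 50% to 100%.

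**Formulas**

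- Displayed percentage = p × (number assessed / analysis-set total).
- Share assessed at week w, up to Week 10: 1 − D × w / 12.
- Share assessed at Week 12 with ET visits pooled in: (1 − D) + a × D.

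**Results for p = 5%, D = 27.1%**

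| Visit | Share assessed | Displayed |
|---|---|---|
| Week 2 | 1 − 0.271 × 2/12 = 0.955 | 4.8% |
| Week 4 | 0.910 | 4.5% |
| Week 6 | 0.865 | 4.3% |
| Week 8 | 0.819 | 4.1% |
| Week 10 | 0.774 | 3.9% |
| Week 12, a = 50% | 0.729 + 0.5 × 0.271 = 0.865 | 4.3% |
| Week 12, a = 100% | 1.000 | 5.0% |

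In an arm of 70, about 54 are assessed at Week 10 (70 × 0.774). The expected number with the event is 54.2 × 0.05 = 2.7. Then 2.7 / 70 = 3.9%, against 2.7 / 54.2 = 5.0% among those assessed.

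**Range over D**

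- D = 10%: Week 10 shows 5% × 0.917 = 4.6%. Week 12 shows 4.75% to 5.0%.
- D = 40%: Week 10 shows 5% × 0.667 = 3.3%. Week 12 shows 4.0% to 5.0%.

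**Unequal drop-out (assumed, both directions)**

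- Active 40% not assessed, placebo 10%: rates of 15% v 10% among those assessed show as 15 × 0.60 = 9.0% v 10 × 0.90 = 9.0%. The excess disappears.
- Active 10% not assessed, placebo 40%: equal rates of 10% show as 9.0% v 6.0%. An excess appears where there is none.

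With participants assessed at the visit as denominator, a constant 5% among those assessed shows as 5.0% at every visit and in every arm.

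**The case against.** The strongest case against is that little depends on these tables. Safety is descriptive only. Adverse events and adjudicated joint events are cumulative, and the stated denominator is participants treated. Every participant with confirmed or symptomatic orthostatic hypotension is listed with all results, and so is every participant with an abnormal ECG. Neurological abnormalities get a key participant information table, and postural blood pressure is also summarised as a continuous variable. All of this stands. A reader might infer that the rule would hide an autonomic or ECG signal in the high-dose arms. The documents do not support that: these outputs limit the risk, and the SAP gives no arm-specific drop-out. Discontinuation for lack of efficacy could as well be higher on placebo.

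Further limits also stand:

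- ECG has a normal category, so its counts add up to the number assessed and the shortfall is visible. Participants without an ECG are not silently counted as normal.
- The 255 is an information-equivalent recruitment threshold tied to completing treatment. It is not a forecast of 73% attendance, and applying 73% to every earlier visit would overstate the loss.
- ECG and neurological visit timing is left to the protocol, so a Week 2 to Week 10 decline cannot be shown for them here.
- The Week 12 rise does not apply to TNSn, whose ET data are reassigned by study day. It does not clearly apply to injection site reactions either, because the last dose is at Week 10.
- A reader might expect a further fall in follow-up. Section 1.2 expects participants who stop treatment to complete follow-up, so this is not shown.

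Two objections stand only in part. Table shells may set another denominator, but they are not at hand and the SAP text does not. And an assessed-only rate describes those still attending, so it too understates risk if participants with events leave. That is a reason to show the number assessed, not to keep a denominator that includes people who were not examined.

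**Conclusion.** The point holds for the by-visit tables of orthostatic hypotension, ECG category and injection site reactions, and for any percentage in the by-visit neurological summary. Followed as written, section 4.1 gives percentages that understate the rate among those assessed by exactly the share not assessed. For orthostatic hypotension the ET pooling adds a rise at Week 12 that need not reflect risk.

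The size is modest. At 27% drop-out accruing linearly, a constant 5% loses about 1.1 percentage points by Week 10 and regains part or all of that at Week 12. These figures rest on assumed drop-out, ET attendance and a constant rate. The effect on arm comparisons depends on drop-out by arm, which the SAP does not give, and could run either way. Adverse event, adjudicated-event, liver and laboratory shift tables are not affected, and no formal test changes.

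**What to change.** Add to SAP section 4.1: *For by-visit categorical summaries, percentages are based on the number of participants in the cohort with a non-missing assessment of that parameter at that visit (for injection site reactions, participants dosed and assessed), and this n is shown.* Leave in place any section that states its own rule, such as the SF-36v2 responder rule in 3.5.1.3, which counts missing data as non-response.

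State in the Week 12 columns how many records are ET visits, because the new denominator alone does not separate them. Keep the analysis-set total for whole-study incidence tables.

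The cost is one sentence, a denominator change in a few table programs and an added count. No new data are needed. The small downside is that the rate then describes participants still attending, which is why the number assessed must stand beside it.
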